12.1.6.4.6. Safety Notifications by the Sponsor to the Investigator

Investigators will receive prompt notification of any suspected adverse drug reaction that is both serious and unexpected, or any finding that suggests a significant risk for patients, in accordance with local laws and regulations. The Investigator will promptly inform his/her IRB/IEC of the notification and insert the notification in the Investigator's Regulatory Binder in accordance with local regulations.

12.2. Assessment of Efficacy

12.2.1. Assessment of MDS Disease

Assessments of the patient's MDS disease will be performed by collection of peripheral blood, bone marrow biopsy and aspirate samples. If the bone marrow biopsy and aspirate are nonproductive or not diagnostic, the procedure must be repeated. Six to 8 bone marrow slides should be prepared (in addition to fresh bone marrow samples) and sent to the designated pathology laboratory for assessment. The patient's disease assessment will be done according to International Working Group Response Criteria for MDS 2006 ([Appendix 6](#)).

12.2.2. Survival

Survival status will be collected every 6 months for at least one year from the first dose of TP-0184 treatment (Cycle 1 Day 1).

12.2.2.1. ECOG Performance Status

Standard criteria as defined by the ECOG Scale of Performance Status ([Appendix 7](#)) will be considered for assessing the patient's level of activities, mobility, and functioning abilities.

12.2.2.2. ECHO/MUGA

ECHO or MUGA scan will be performed as primary cardiac monitoring to assess LVEF, as specified in [Table 6](#). If an ECHO or MUGA have been obtained within 6 weeks of EOT, they do not need to be repeated.

12.2.2.3. MRI Imaging

Cardiac and hepatic imaging by MRI for quantification of iron will be performed as specified in the Schedule of Assessments. The MRI may also be performed ad hoc if signs/symptoms of iron overload are noted. Please reference study specific MRI Acquisition Manual.

12.2.2.4. New York Heart Association Classification

The NYHA ([Appendix 11](#)) provides a simple way of classifying the extent of heart failure. It classifies patients in 1 of 4 categories based on their limitations during physical activity; the limitations/symptoms are with regard to normal breathing and varying degrees in shortness of breath and or angina pain.

12.2.3. Patient Reported Outcomes

The Brief Fatigue Inventory (BFI; see [Appendix 10](#)) is a brief participant-reported questionnaire that measures the severity of fatigue based on the worst fatigue experienced during the past 24 hours. The severity of fatigue is assessed using an 11-point numeric scale, with 0 = no fatigue and 10 = fatigue as bad ([Mendoza 1999](#)). Patients will complete a paper version of this questionnaire at screening, Day 1 of each cycle, at EOT and follow-up.

13. STATISTICS

13.1. Statistical Methods

Detailed methodology for the statistical analyses of the data collected in this study will be documented in the statistical analysis plan (SAP), which will be maintained by SDP Oncology. The SAP may modify the plans outlined in the protocol; however, any major modifications of the primary endpoint definition and/or its analysis will also be reflected in a protocol amendment.

13.1.1. Determination of Sample Size

13.1.2. Phase 1

The exact sample size for Phase 1 (dose escalation part) cannot be specified in advance due to the dynamic features of BLRM study design. Approximately 30 patients are planned to be enrolled in Phase 1.

13.1.3. Phase 2

A total of 10 to 60 patients will be enrolled into Expansion Phase 2. After the first 10 enrolled patients are evaluable for efficacy (Efficacy Evaluable Analysis Set), response rate monitoring using Bayesian posterior probability will be performed. If posterior probability of response rate less or equal than 5% is greater than 90% ($\text{Prob } (\theta \leq 0.05) > 0.90$), the study may be stopped for futility; if posterior probability of response rate greater or equal than 20% is greater than 80% ($\text{Prob } (\theta \geq 0.2) > 0.80$) during study enrollment, SDP Oncology has the option to stop the enrollment of Phase 2 and trigger subsequent clinical development of TP-0184. If neither criterion is met, it will continue to more fully characterize the response rate in a total of approximately 60 efficacy evaluable patients. If posterior probability of response rate greater or equal than 20% is greater than 50% ($\text{Prob } (\theta \geq 0.2) > 0.50$) at the final analysis, the current study will be considered to be successful.

13.1.4. Randomization and Stratification

There is no randomization in this study.

13.1.5. Analysis Datasets

The safety analysis set (SAS) is defined as all patients who receive at least one dose of study drug (TP-0184) and will be used for safety analysis and related time to event analyses if applicable.

The DLT analysis set (DAS) is defined as patients evaluable for the determination of dose escalation in Phase 1 who met either one of the following criteria:

1. Experienced a DLT during the first 28 days (the DLT evaluation period)
2. Completed the DLT evaluation period and received at least 80% of planned doses.

Patients who did not meet either of the above criteria are not evaluable for the dose escalation assessment and may be replaced as needed to permit dose escalation. The DAS will be used for DLT related analysis.

The efficacy evaluable analysis set (EAS) is defined as all patients who have baseline data of Hemoglobin value, number of transfusions received in previous 12 weeks before study treatment, have received at least 1 dose of TP-0184, and have at least 1 available post baseline response assessment as per the composite endpoint criteria. The EAS will be used for analyses of response rate and related efficacy analyses.

Pharmacokinetic evaluable analysis set is defined as all treated patients in the trial with sufficient and adequate PK sample data as determined by SDP Oncology.

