After completing a given dose escalation cohort, the decision to move up to the next cohort or not, or to adjust to a lower or slightly higher dose, will be decided by the SRC based on BLRM with EWOC and integration of all available safety data, PK and other clinical data using the BLRM method. The dose recommended using the BLRM method will serve as a guide and will be integrated with clinical assessment of the safety information and review of other available data to determine the actual treatment dosage.

Additional or intermediate dose levels may be explored. It is possible that potential arm with different dosing schedule is added during the Phase I study period based on safety considerations.

Determination of Recommended Dose:

The recommended dose is usually the dose with acceptable toxicity, generally defined as the dose level producing a DLT rate within the toxicity interval (16%, 33%). Determination of the recommended dose will be performed in consultation with the SRC based on safety and other data available at the time of the recommended dose decision.

Once the recommended dose for the expansion arms is identified, the Phase 1 portion of the study will progress to Phase 2.

Phase 2:

The Phase 2 design is based on Bayesian efficacy monitoring using posterior probability criteria. After the first 10 enrolled patients are evaluable for efficacy (Efficacy Evaluable Analysis Set), response rate monitoring using Bayesian posterior probability will be performed. If posterior probability of response rate less or equal than 5% is greater than 90% ($\text{Prob } [\theta \leq 0.05] > 0.90$), the study may be stopped for futility; if posterior probability of response rate greater or equal than 20% is greater than 80% ($\text{Prob } (\theta \geq 0.2) > 0.80$) during study enrollment, SDP Oncology has the option to stop the enrollment of Phase 2 and trigger subsequent clinical development of TP-0184. If neither criterion is met, it will continue to more fully characterize the response rate in a total of approximately 60 efficacy evaluable patients. If posterior probability of response rate greater or equal than 20% is greater than 50% ($\text{Prob } [\theta \geq 0.2] > 0.50$) at the final analysis, the current study will be

considered successful. Efficacy as assessed by response rate will be monitored using the Bayesian posterior probability to optimize the enrollment with Bayesian stopping rules.

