6. STUDY OBJECTIVES AND ENDPOINTS

6.1. Primary Objectives and Endpoints

Primary Objectives	Study Endpoints
Phase 1	

 • To assess the safety and tolerability of TP-0184 • To determine the maximum tolerated dose (MTD) or maximum administered dose (MAD) and recommended dose for the future expansion arms of TP-0184 in the Phase 2 part of the study 	Assessment of dose limiting toxicities (DLTs), treatment-emergent adverse events (TEAEs); type, frequency and severity of AEs and relationship of AEs to TP-0184, TP-0184 dose interruptions and dose reductions
Phase 2	
To determine the effect of TP-0184 on the treatment and the hematologic improvement of anemia in terms of hemoglobin increase, reduction in RBC transfusions and Transfusion-Free \geq 8 weeks	
Response rate based on composite response criteria:
 
Hemoglobin increase \geq 1.5 g/dL maintained for a consecutive period of 8 weeks with no transfusions
 
OR
 
Reduction in units of \geq 4 RBC transfusions / 8 weeks (consecutive) compared with the pretreatment transfusion number in previous 8 weeks
 
OR
 
Patients who are RBC transfusion-free over any consecutive 8-week (56-day) period

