13.1.9.1.2. Phase 2 Efficacy Analysis

13.1.9.1.2.1. Response Rate

Response rate is defined as the proportion of patients who achieves response according to the composite endpoint criteria for a consecutive period of 8 weeks ([Appendix 1](#)). Response rate will be estimated with 2-sided 95% exact binomial confidence intervals based on EAS.

13.1.9.1.2.2.12-Week Response Rate

The 12-Week response rate is defined as the proportion of patients who achieves response according to the composite endpoint criteria for a consecutive period of 12 weeks ([Appendix 1](#)). The 12-Week response rate will be estimated with 2-sided 95% exact binomial confidence intervals based on the EAS.

13.1.9.1.2.3. Time to RBC transfusion-free analysis

Time to RBC transfusion-free period is defined as the time from the date of initial dosing at RP2D to first documentation of a transfusion-free period for patients who have one or more transfusion-free periods. Transfusion-free period is defined as the period that a patient becomes transfusion-free for consecutive 8 weeks or longer after treatment of TP-0184. Kaplan-Meier (K-M) survival curve and K-M median (estimate), along with 2-sided 95% CIs, will be provided.

13.1.9.1.2.4. Duration of Hemoglobin Response

Duration of hemoglobin response is defined as the time from the date of first documentation of a hemoglobin response to the date of first documentation of progression of hemoglobin response for hematologic responders. Hemoglobin response is defined as an increase ≥ 1.5 g/dL maintained for a consecutive period of > 8 weeks with no transfusions; hemoglobin progression is defined as a change from baseline < 1.5 g/dL of the hemoglobin or the start of one or more transfusions.

The K-M survival curve and K-M median (estimate), along with 2-sided 95% CIs will be provided.

13.1.9.1.2.5. Duration of Reduction in RBC Transfusion for 8 Weeks Analysis

High transfusion burden patient with reduction in RBC transfusion for 8 weeks is defined as high transfusion burden patients (baseline ≥ 4 U transfusions) patients with change from baseline of equal or more than 4 units transfusions in consecutive 8 weeks in EAS.

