20. APPENDICES

**APPENDIX 1. CONSIDERATION OF RESPONSE FOR COMPOSITE
ENDPOINT**

Patient population	Hemoglobin increase ≥ 1.5 in the absence of transfusion / 8 weeks	RBC transfusion free / 8 weeks	Reduction in units of ≥ 4 RBC transfusions / 8 weeks
High transfusion burden (≥ 4 U transfusion)	X	X	X
Low transfusion burden (1-3 U transfusion)	X	X	

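### The Phase 2 response rate and Bayesian rules use an efficacy set whose entry condition is undefined, so the plan does not fix who is in the denominator

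*Protocol*

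**What the plan says.** Protocol Section 13.1.5 admits a patient to the EAS who has baseline hemoglobin and transfusion data, has taken at least one dose, and who must also "have at least 1 available post baseline response assessment as per the composite endpoint criteria". Neither document says what such an assessment is.

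The set carries the primary analysis. Section 13.1.9.1.2.1 defines a responder as a patient who "achieves response according to the composite endpoint criteria for a consecutive period of 8 weeks" and adds: "Response rate will be estimated with 2-sided 95% exact binomial confidence intervals based on EAS". Section 13.1.3 starts monitoring from the same set: "After the first 10 enrolled patients are evaluable for efficacy (Efficacy Evaluable Analysis Set), response rate monitoring using Bayesian posterior probability will be performed". The final success rule, in the Synopsis and Sections 13.1.3 and 13.1.9, applies at about 60 patients.

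Every component of the composite needs 8 weeks. Section 6.1 lists, for example, "Patients who are RBC transfusion-free over any consecutive 8-week (56-day) period", and the corresponding column in Appendix 1 reads "RBC transfusion free / 8 weeks".

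Section 13.1.6 leaves missing data missing unless another rule is given, and none is given for response. Section 13.1 defers detail to the SAP, but SAP Section 2 reports termination after two patients and plans listings only.

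The number 60 has two meanings. Section 13.1.3 says "A total of 10 to 60 patients will be enrolled into Expansion Phase 2", while the same section and the Synopsis say that, without an early stop, "it will continue to more fully characterize the response rate in a total of approximately 60 efficacy evaluable patients". Section 7.2.1 covers replacement only for patients outside the DLT analysis set.

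**The concern.** Two readings of the entry condition are open, and they pull in different directions.

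- **Completed window.** The reference to the composite criteria suggests an assessment that can be judged against them, and that takes 8 weeks. Patients who die, withdraw or are lost before then drop out of the denominator. Selection is then on a post-treatment event linked to failure, and a single-arm rate compared with a fixed 20% is biased upward.
- **One early record.** The words requiring at least one assessment suggest that a single post-baseline hemoglobin or transfusion record is enough. Almost every treated patient then counts at the final analysis. Monitoring, however, runs during enrolment, so a patient dosed a few weeks earlier is already in the set and cannot yet have an 8-week response. Interim rates are then biased downward.

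At stake are the primary estimate, the option to stop enrolment early and the final success call, in an open-label trial where the choice of reading could be made with the data in view.

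**Working it through.** **Inputs from the protocol.** Final success if Prob(θ ≥ 0.20) > 0.50 at about 60 patients. Option to stop enrolment if Prob(θ ≥ 0.20) > 0.80, from 10 evaluable patients on (Section 13.1.3). The plan gives no Phase 2 prior, loss rate, response boundary or operating characteristics, so there is no stated figure to reproduce.

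**Assumptions.** Priors Beta(1,1), Beta(0.5,0.5) and Beta(0.2,0.8). A share d = 5% or 10% of treated patients is lost before a completed window, and none of them is a responder. With x responders in n patients and prior Beta(a,b), the posterior is Beta(a + x, b + n − x).

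**Step 1: who is lost under the completed-window reading.** Table 6 collects transfusion data until 30 days after the last dose or the end-of-treatment visit, whichever is later. Thirty days is therefore a minimum. A patient dosed to about day 26 and followed as planned has 26 + 30 = 56 days of transfusion data, enough to judge the transfusion-free component. Those left out are mainly patients who stop in about the first four weeks, or who die, withdraw consent or are lost without later follow-up.

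**Step 2: the final boundary.** Sixty evaluable patients correspond to 60/0.95 ≈ 63 or 60/0.90 ≈ 67 treated.

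| Prior | Responders needed, n = 60 | n = 63 | n = 67 |
|---|---|---|---|
| Beta(1,1) | 12 | 13 | 13 |
| Beta(0.5,0.5) | 12 | 13 | 14 |
| Beta(0.2,0.8) | 13 | 13 | 14 |

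Uniform prior, same 12 responders:

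- 12/60 = 20.0% (exact 95% CI 10.8 to 32.3%), Prob(θ ≥ 0.20) = 0.551: success.
- 12/67 = 17.9% (CI 9.6 to 29.2%), Prob = 0.380: failure.

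At 5% loss, 12/63 gives 0.475 (uniform) and 0.437 (Beta(0.5,0.5)), both failures. Under Beta(0.2,0.8), 13/63 still passes at 0.525.

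**Step 3: chance of meeting the final rule.** Take a true response rate of 16% in all treated patients, recruitment to 60 evaluable, and the final look only. The rate within the EAS is 0.16/(1 − d): 0.16/0.95 = 16.8% and 0.16/0.90 = 17.8%. For the all-treated analysis the number treated varies with the number lost, and the boundary is recomputed for each total. Differences were taken before rounding.

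| Prior | 5% loss: EAS v all treated | Added (points) | 10% loss: EAS v all treated | Added (points) |
|---|---|---|---|---|
| Beta(1,1) | 30.5% v 24.0% | 6.5 | 37.7% v 23.1% | 14.5 |
| Beta(0.5,0.5) | 30.5% v 19.7% | 10.8 | 37.7% v 19.5% | 18.1 |
| Beta(0.2,0.8) | 20.1% v 18.4% | 1.7 | 26.1% v 17.8% | 8.2 |

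**Step 4: interim looks.** Under a uniform prior, 3/10 gives Prob(θ ≥ 0.20) = 0.839, above 0.80, and 3/11 gives 0.795, below it. The eleventh patient may be an early failure left out under the completed-window reading, or a recently dosed patient admitted too soon under the early-record reading. The reversal is specific to that prior: 3/10 gives 0.795 under Beta(0.5,0.5) and 0.728 under Beta(0.2,0.8), so the rule is not met there in any case.

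**Step 5: the meaning of 60.** If 60 is the number treated and 10% are lost, the EAS holds 54. Uniform prior: 11/54 gives 0.580 (success) and 11/60 gives 0.424 (failure).

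**The case against.** An evaluable set is a legitimate planned choice for a preliminary efficacy estimate, and defining the term would remove the ambiguity. Few patients may be lost: entry requires low or intermediate risk disease and a life expectancy of at least 3 months, and the 30-day minimum of transfusion collection keeps most of those who stop after week four. The 5% and 10% loss rates have no support in the documents. All of this stands as a limit on size. It does not settle the matter, because a definition alone could still confirm a denominator selected on a post-treatment event.

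Three stronger readings are tempting and not supported.

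- A reader might infer that the plan does exclude early failures. It does not say so; the early-record reading is equally open.
- A reader might infer that on the early-record reading nothing is wrong. That holds only for the final analysis; interim rates are then too low.
- A reader might count every early efficacy stop as success and attribute the high chance of success to the EAS. Section 13.1.3 gives the sponsor only an option to stop enrolment and defines success only at the final analysis. With no loss at all and a uniform prior, counting those stops raises the chance at a true 16% from 24.5% to 41.0%; that comes from repeated looks, not from the EAS.

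**Conclusion.** The point holds as a flaw in the written plan. An undefined term decides who is counted in the primary endpoint, and no rule makes treated patients without an assessment non-responders. The direction of bias depends on the reading and the look: upward under the completed-window reading, downward at interim looks under the early-record reading, and close to nil at the final analysis under the latter.

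The size is conditional on an assumed prior, an assumed loss rate and lost patients being non-responders. Only results near the cut-off change. At a true rate of 16% and the final look alone, the EAS adds 1.7 to 10.8 points to the chance of success at 5% loss and 8.2 to 18.1 at 10%. One might infer that a reported result is in doubt; none is, because the study ended after two patients and the SAP plans no efficacy analysis. The correction matters if the design is reused.

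**What to change.** - Make the primary response set all Phase 2 patients who receive at least one dose at the RP2D. At the final analysis, count those without a documented 8-week response as non-responders. Keep the EAS as a supportive analysis and define its response assessment.
- At each interim look, include patients by time since first dose, with one minimum follow-up stated in advance and applied alike to patients who have left and those who continue, so that failures do not enter before responders. It must exceed 8 weeks, because a response may fall in any consecutive 8-week period. The planned 24 weeks is not a strict upper bound, since Sections 7.3.1 and 8.3.1 let treatment continue beyond it; the sponsor should weigh the length against later looks.
- State whether 60 means treated or evaluable patients, and whether lost patients are replaced.

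The cost is text in the Synopsis and Sections 13.1.3, 13.1.5, 13.1.9 and 13.1.9.1.2.1, with no new data. The response rate becomes slightly less favourable, and interim looks come later, which makes the monitoring slower to act on enrolment.

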13.1.6. Handling of Missing Data

All available efficacy and safety data will be included in data listings and tabulations. Data that are potentially spurious or erroneous will be examined under the auspices of standard data management operating procedures.

In general, missing data will be treated as missing and no data imputation will be applied, unless otherwise specified. For patient reported outcomes data, primarily missing data imputation will be based on published instrument specific methods. Other missing data imputation method such as Last Observation Carry Forward (LOCF) and mixed model may be explored as sensitivity analyses for patient reported outcomes data.

13.1.7. Demographic and Baseline Characteristics

The demographic and baseline characteristics will be summarized in a descriptive fashion. Data to be evaluated will include age, sex, race, weight, baseline disease characteristics, and other parameters, as appropriate.

13.1.8. Data Analyses

13.1.8.1. Phase 1

Two-parameter Bayesian logistic regression model (BLRM) with EWOC will be used to guide dose escalation and estimate the MTD based on occurrence of DLT during Cycle 1. MTD with estimated posterior probability of a DLT within target toxicity interval (16%, 33%) among the admissible doses fulfilling EWOC is determined by BLM. MTD is estimated based on observed DLTs.

After completing a given dose escalation cohort, the decision to move up to the next cohort or not, or to adjust to a lower or slightly higher dose, will be decided by the SRC based on BLM with EWOC and integration of all available safety data, PK, and other clinical data using the BLM method. The dose recommended using the BLM method will serve as a guide and will be integrated with clinical assessment of the toxicity information and review of other available data to determine the actual treatment dosage.

Additional or intermediate dose levels may be explored after the discussion and concurrence of SRC and SDP Oncology clinical team. It is possible that potential arm with different dosing schedule is added during the Phase I study period based on safety considerations.

13.1.8.2. Determination of Recommended Dose

The recommended dose is usually the dose with acceptable toxicity, generally defined as the dose level producing a DLT rate within the toxicity interval (16%, 33%). Determination of the

recommended dose will be performed in consultation with the SRC based on safety and other data available at the time of the recommended dose decision.

Once the recommended dose for the expansion arms is identified, the Phase 1 portion of the study will progress to Phase 2.

